6.5. Study Drug Administration

Study drug exposure through Week 52 will be summarized [T1.20]. Duration of exposure (days) (see Section 13.4.2) and the total number of injections will be summarized using continuous summary statistics. The total number of injections will also be categorized as 1 - 12, 13 - 24, 25 - 36, 37 - 51 or >51.

A listing of all injections will be presented by subject, including injection number, dosing cohort, and some additional details if the injection has been given [L1.11].

6.6. CRF Listing

A spreadsheet will be created that identifies which subjects in the study should have Case Report Forms (CRFs) included in the submission for each Country [L6]. The following Countries and criteria for CRF inclusion will be implemented:

- United States: Death, Study Withdrawals Due to AEs (Serious and Non-Serious), i.e. the default criteria
- Canada: Death, Study Withdrawals Due to AEs, Serious Adverse Events, i.e. the default criteria
- China: Does not require CRFs, therefore no criteria will be applied and the column will be left blank
- Japan: Does not require CRFs, therefore no criteria will be applied and the column will be left blank
- European Union: Does not require CRFs, therefore no criteria will be applied and the column will be left blank

7. EFFICACY ANALYSES

Efficacy will be evaluated by the exploratory endpoint (≥ 4 point reduction from baseline in SELENA SLEDAI at Weeks 12 and 52) and the other efficacy endpoints of interest (including other SELENA SLEDAI summaries, proteinuria and prednisone summaries).

The efficacy tables and figures will be based on the ITT population and the listings will be based on the enrolled population, unless otherwise specified. See 'RAP mock outputs 200908' document for mock displays.

Efficacy outputs will report all observed On Study data (see Section 5.2). Efficacy data will be summarised using a treatment policy approach, including all data regardless of any Intercurrent Events (ICE).

7.1. Exploratory Efficacy Analyses

7.1.1. Summary Measure

The percentage of subjects with \geq 4-point reduction from baseline in SELENA SLEDAI at Weeks 12 and 52.

7.1.2. Population of Interest

The exploratory efficacy analyses will be based on the ITT population.

7.1.3. Subgroup, Supportive and Sensitivity Analyses

Summaries will be presented by baseline weight cohort and overall. There are no planned supportive or sensitivity analyses for the exploratory efficacy endpoints. Posthoc analyses may be considered for other subgroups.

7.1.4. Statistical Methodology Specification

The number and percentage of subjects with \geq 4-point reduction from baseline in SELENA SLEDAI at Weeks 12 and 52 will be provided using the observed data. Each of the three cohorts will be summarized separately and overall [T2.01]. No statistical tests will be performed.

Summary statistics will be provided for SELENA SLEDAI percentage change from baseline by visit for each of the three cohorts and overall [T2.02] and change from baseline by visit for each of the three cohorts and overall [T2.03] using the observed data. No statistical tests will be performed.

A line graph will be produced to show the percentage (±SE) of subjects who have at least a 4-point reduction from baseline in SELENA SLEDAI by visit using the observed data for all subjects [F2.01], as well as by cohort [F2.04].

A listing of SELENA SLEDAI analysis results for each subject will be provided by visit. The listing will include SELENA SLEDAI total score, change and percentage change from baseline in total score [L2.01].

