2.2.1. Study of IV Belimumab in Pediatric SLE Study Participants

BEL114055 is the first randomized placebo-controlled trial to test for treatment effect on disease activity outcomes in pediatric SLE. BEL114055 is a three-part study. In Part A (52-week double-blind treatment phase), participants were randomized to receive IV belimumab or placebo in addition to standard of care SLE therapy. Participants who completed Week 52 of Part A were eligible to participate in Part B, a 10-year open-label continuation phase. Participants discontinuing study agent in Part A or Part B were eligible for enrollment into Part C, the long-term safety follow-up phase. Parts B and C are ongoing. Part A was completed in January 2018. Due to the rarity of SLE in children and the resulting recruitment challenges, BEL114055 was not powered by design, and therefore no hypothesis testing was performed. Of the 93 participants enrolled in BEL114055, 40 participants were randomized to placebo and 53 participants to IV belimumab in Part A. Thirteen participants were 5 to 11 years of age and 80 participants were 12 to 17 years of age at the time of screening. Within the limits of the 1-year data analyzed to date, the risk/benefit profile of IV belimumab 10 mg/kg in pediatric SLE patients appears consistent with that of the adult patient population.

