4.3. Justification for Dose

The dose and dosing regimens selected for SC administration in this pediatric population are intended to achieve a similar average exposure as observed with the weekly 200 mg SC dosing regimen in adult SLE patients, estimated at 104 μ g/mL from a population PK analysis of SC study data in adults [GSK Document Number [2015N263802_01](#)].

For a fixed belimumab dose the exposure increases as body weight decreases, as observed in adults and supported by the population PK model developed from the pediatric IV study BEL114055. To accommodate children between the ages of 5 to 17, specifically to ensure lower body weight subjects are not over-exposed, three belimumab SC dose groups are proposed and defined by body weight. Pediatric subjects weighing 50 kg or more will receive 200 mg belimumab once a week (QW), as per the recommended dosing regimen in adults. Pediatric participants who weigh between 30 to 50 kg will receive as 200 mg belimumab administered once every ten days (Q10d). Pediatric participants weighing less than 30 kg will receive 200 mg belimumab once every two weeks (Q2W).

The proposed 30 and 50 kg weight thresholds approximately correspond to the age groups 5-9 years, 9-14 years, and 14 years or older - according to the CDC growth chart 9.3 and 14.2-year-old girls have median weights of 30.1 and 50.0 kg, respectively. [https://www.cdc.gov/growthcharts/clinical_charts.htm#Set1].

[figure not shown]
The pediatric population PK model for IV administration, developed from the pediatric IV study data (BEL114055 CSR), was extended to include SC dosing by incorporating the absorption components of the adult SC PK model [GSK Document Number [2015N263802_01](#)]. The resulting model was used to simulate the three dose groups for 200 mg SC: (1) Q2W for <30 kg; (2) Q10d for \geq 30 kg and <50 kg; (3) QW for \geq 50 kg subjects. The simulations sampled a pediatric population biased towards females (90%) which is typical of an SLE population. Body size parameters (body weight and BMI) were sampled from the NHANES 2015-2016 database and restricted to pediatric subjects between the ages of 5 and 18 years. Other covariates which form model input parameters were sampled from the pediatric study BEL114055 dataset.

For the proposed dosing regimen, the range of exposures in the three dose groups (Q2W <30kg, Q10d \geq 30 to <50kg, QW \geq 50kg) are very similar ([Figure 1](#), [Table 1](#)). At the 30

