7.2.2.2. Average Daily Prednisone Dose Between Visits

The average daily prednisone dose between visits will be calculated for each scheduled post-baseline visit by summing all prednisone doses since the previous visit (previous visit date +1) up to and including the current visit and then dividing by the number of days in this period (Date of current visit – Date of previous scheduled visit). Days on which a subject does not have prednisone use recorded will be considered as 0 mg for the day in the calculation of average daily prednisone dose.

For subjects who withdraw from the study, the early withdrawal visit will only be presented if it slots into a scheduled visit (see Section 13.1.1).

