9. PHARMACOKINETIC ANALYSES

9.1. Primary Pharmacokinetic Analyses

The PK analyses will be based on the PK population. See 'RAP mock outputs 200908' document for mock displays.

PK outputs will report all On Study data (see Section 5.2). On-treatment PK data will be summarised using a treatment policy approach, including all data regardless of any Intercurrent Events (ICE). Week 8 Follow Up data will only be summarised if the subject has stopped their study treatment and hasn't taken any concomitant Belimumab during the follow-up period.

Descriptive statistics for observed belimumab concentrations will be displayed for each scheduled visit where pre-dosing PK samples are available for analysis. Each of the three cohorts will be summarized separately and overall [T5.01], and the following statistics will be displayed: number of subjects, mean value, standard deviation, 95% confidence interval, geometric mean, geometric standard deviation, geometric 95% confidence interval, geometric coefficient of variation (%), median, 25th and 75th percentiles, minimum, and maximum. No statistical tests will be performed.

The geometric mean, standard deviation and confidence interval are calculated at each visit using all of the non-zero PK concentration values. These non-zero concentration values are log transformed and the arithmetic mean, standard deviation and confidence interval are calculated. The geometric mean, geometric standard deviation and geometric confidence intervals are the exponentials of these values.

The geometric Coefficient of Variation is calculated as follows:

$$CV(\%) = \sqrt{exponential(logSD^2) - 1} * 100$$

where logSD is the standard deviation of the log-transformed concentrations.

A graph will be produced which displays the median pre-injection belimumab concentrations (+/- interquartile range) by visit through Week 52 for all subjects [F5.01], as well as by cohort [F5.02].

Additionally, a line graph will be produced which displays the geometric mean preinjection belimumab concentrations (with 95% Confidence Interval) by visit through Week 52 for all subjects [F5.03], as well as by cohort [F5.04].

A listing of belimumab PK concentration-time data will be presented by subject [L5.01].

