13. APPENDICES

13.1. Appendix 1: Assessment Windows

13.1.1. Definitions of Assessment Windows for Analyses

The data is analysed as per the planned visit assignment.

Exit/withdrawal and unscheduled visits will be slotted to the appropriate planned visit. The assigned visit is based on the interval in which the Study Day for the exit/withdrawal or unscheduled visit falls according to intervals (inclusive) provided below. For completeness, the table also includes visits which are not slotted; these visits will have 'N/A' for 'not available' listed for the Interval Start and End Day.

Analysis	Parameter	Target ¹	Analysis	Analysis Window		Analysis Timepoint
Set / Domain	(if applicable)		Beginning Timepoint	Ending Timepoint	Timepoint Number	
All	NA	Day -35	N/A	N/A	10	Screening
Cohort 1 ar	d Cohort 3	_L			I.	
All	All	Day 1	N/A	N/A	20	Week 0 (Day 1)
		Day 8	2	11	30	Week 1 (Day 8/11)
		Day 15	12	21	40	Week 2 (Day 15/21)
		Day 29	22	42	50	Week 4 (Day 29/31)
		Day 57	43	70	60	Week 8 (Day 57/61)
		Day 85	71	98	70	Week 12 (Day 85/81)
		Day 113	99	126	80	Week 16
		Day 141	127	154	90	Week 20
		Day 169	155	189	100	Week 24
		Day 211	190	231	110	Week 30
		Day 253	232	280	120	Week 36
		Day 309	281	336	130	Week 44
		Day 365	337	378	140	Week 52
		Day 421	N/A	N/A	175	8 Week Follow-up ²
		Day 477	N/A	N/A	185	16 Week Follow-up ³
Cohort 2						
All	All	Day 1	N/A	N/A	20	Week 0 (Day 1)
		Day 11	2	15	30	Week 1 (Day 8/11)
		Day 21	16	25	40	Week 2 (Day 15/21)
		Day 31	26	45	50	Week 4 (Day 29/31)
		Day 61	46	70	60	Week 8 (Day 57/61)
		Day 81	71	96	70	Week 12 (Day 85/81)
		Day 113	97	126	80	Week 16
		Day 141	127	154	90	Week 20
		Day 169	155	189	100	Week 24

CONFIDENTIAL

200908

Analysis Parameter Set / (if Domain applicable)		Target ¹	Analysis Window		Analysis	Analysis Timepoint
			Beginning Timepoint	Ending Timepoint	Timepoint Number	
		Day 211	190	231	110	Week 30
		Day 253	232	280	120	Week 36
		Day 309	281	336	130	Week 44
		Day 365	337	378	140	Week 52
		Day 421	N/A	N/A	175	8 Week Follow-up ²
		Day 477	N/A	N/A	185	16 Week Follow-up ³

Note:

¹ Study Day with Baseline/Treatment Start Date as Day 1.

²The 8-week follow-up occurs 8 weeks after Week 52, or 8 weeks after early withdrawal or 8 weeks after last dose for subjects who withdraw from Part A and do not enter Part B.

³ The 16-week follow-up occurs 16 weeks after Week 52, or 16 weeks after early withdrawal or 16 weeks after last dose for subjects who withdraw from Part A and do not enter Part B.

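### SELENA SLEDAI response displays: ±SE bars vanish at 0/n or n/n in a small weight cohort, and visit slotting can add values made only of withdrawal or unscheduled scores

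*SAP*

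**What the plan says.** The endpoint is the percentage of participants whose SELENA SLEDAI score falls by at least 4 points from baseline, at Weeks 12 and 52 (Protocol section 3). SAP 7.1.4 plans these displays:

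- **T2.01:** the number and percentage with this "reduction from baseline in SELENA SLEDAI at Weeks 12 and 52 will be provided using the observed data", for each weight cohort and overall. No interval is given.
- **T2.02 and T2.03:** percentage change and change in score, by visit, for each cohort and overall.
- **F2.01 and F2.04:** "A line graph will be produced to show the percentage (±SE) of subjects who have at least a 4-point reduction from baseline", by visit on observed data, for all participants and by cohort respectively.
- **L2.01:** each participant's scores by visit.

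The protocol's Schedules of Activities place post-baseline SELENA SLEDAI only at Week 12 (Day 85, or Day 81 in Cohort 2) and Week 52. An early withdrawal visit carries the same assessments as whichever of these two visits closes that part of the study.

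SAP 13.1.1 has one set of windows for all domains and parameters: "Exit/withdrawal and unscheduled visits will be slotted to the appropriate planned visit".

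**The concern.** An error bar tells the reader how far to trust a point. The usual standard error of a proportion is exactly zero when nobody or everybody responds, so the bar disappears. In a cohort of a few children, that is where uncertainty is greatest.

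The second issue is what is plotted. The endpoint has two time points, but the figures and two of the tables run by visit. A child who withdraws around Day 170 has a SLEDAI score taken, and 13.1.1 sends it to Week 24. No other child has a scheduled score there. The figure would then join the Week 12 and Week 52 points, which represent everyone scored, through a point made of one withdrawal. A reader could take that for a time course.

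This is the only efficacy endpoint defined in the protocol. In a descriptive study the displays are what most readers will use.

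**Working it through.** **Inputs from the documents.** About 28 enrolled and 24 evaluable at Week 12 (Protocol 9.2). The stated screening number is reproduced closely: 28/0.8 = 35 against 36. The plan gives no figure for the precision of the response percentage, so there is nothing else to reproduce.

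**Inputs assumed.** Cohort sizes are not stated. One rough guide to Cohort 3 is the age mix of the earlier pediatric IV study: "Thirteen participants were 5 to 11 years of age and 80 participants were 12 to 17 years of age". Applied to 28 children, 28 x 13/93 = 3.9 aged 5-11. Protocol 4.3 links weight to age: "The proposed 30 and 50 kg weight thresholds approximately correspond to the age groups 5-9 years, 9-14 years, and 14 years or older". The lightest cohort is thus the narrower 5-9 band, which suggests about 4 or fewer. Because this borrows another trial's age mix, a range of n is shown. True response rates of 50% and 70% are also assumed.

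**Step 1: zero-width bars.** The formulas are:

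- SE = sqrt(p(1-p)/n), which is 0 at p = 0 or 1 for every n (assumed; the SAP gives no formula)
- Exact (Clopper-Pearson) 95% upper limit at 0/n = 1 - 0.025^(1/n); the lower limit at n/n = 0.025^(1/n)
- Chance of a zero-width bar at true rate p = p^n + (1-p)^n

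| n | Exact 95% CI at 0/n | Exact 95% CI at n/n | Chance, p = 50% | Chance, p = 70% |
|---|---|---|---|---|
| 3 | 0-70.8% | 29.2-100% | 25.0% | 37.0% |
| 4 | 0-60.2% | 39.8-100% | 12.5% | 24.8% |
| 6 | 0-45.9% | 54.1-100% | 3.1% | 11.8% |
| 8 | 0-36.9% | 63.1-100% | 0.8% | 5.8% |
| 24 | 0-14.2% | 85.8-100% | 0.0% | 0.0% |

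For example, at n = 3 and p = 0.7: 0.343 + 0.027 = 0.370. The problem belongs to small cohorts in F2.04. With about 24 children it is negligible in F2.01 at Weeks 12 and 52.

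**Step 2: values at visits without a scheduled score.**

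- SAP 13.1.1 defines 12 contiguous post-baseline windows covering Days 2-378: Weeks 1, 2, 4, 8, 12, 16, 20, 24, 30, 36, 44 and 52.
- SLEDAI is scheduled at two of these, which leaves 12 - 2 = 10.
- In Cohorts 1 and 3, a withdrawal or unscheduled score on Days 2-70 goes to Weeks 1-8, and one on Days 99-336 to Weeks 16-44. In Cohort 2 the second range starts at Day 97.
- SAP 13.5.2 drops a visit from a table when all its data are missing. One of these 10 visits therefore appears only if at least one such score lands there.
- Whatever appears consists entirely of withdrawal or unscheduled scores. If it is a single child, the usual SE is again zero, even in F2.01, while the exact interval at 0/1 is 0-97.5%.

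**The case against.** The strongest reply is that little is at risk. The endpoint is exploratory, nothing is tested, and T2.01 prints counts by cohort, so 3/3 will be seen as 3/3. The SAP also uses ±SE in its prednisone and laboratory figures. The plotted visits and the n under the axis may be specified in the mock outputs, which are not among the documents. Protocol 7.2 expects withdrawal to be uncommon, and children who decline Part B after the Week 12 visit create no off-schedule score. All of this stands and keeps the point small. It does not make a zero-width bar informative, nor does it supply a rule in 7.1.4 on which visits are shown.

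The SAP does plan by-cohort PK figures of "geometric mean preinjection belimumab concentrations (with 95% Confidence Interval) by visit through Week 52". Concentration is a primary endpoint, so this shows only that by-cohort intervals are practicable in this report.

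Three stronger readings are tempting and are not supported:

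- **A safeguard used for prednisone is missing here.** A reader might infer this from SAP 7.2.2.2, where "the early withdrawal visit will only be presented if it slots into a scheduled visit (see Section 13.1.1"). But the windows it points to cover every day from 2 to 378, so copying the sentence into 7.1.4 would exclude nothing within that period.
- **Off-schedule points are likely because most study days fall in windows without a scheduled score.** That is calendar coverage. It gives neither a probability nor an expected number of points.
- **The absence of missing-score bounds is an error.** SAP 7.1.3 is open about it: "There are no planned supportive or sensitivity analyses for the exploratory efficacy endpoints". With N by cohort in T1.08 and the number scored in T2.03, the width between worst and best case is (N - n)/N, one subtraction from planned tables. Adding bounds is optional.

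**Conclusion.** The point holds as a minor correction to how results are displayed.

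- **Error bars.** In F2.04, ±SE can show no uncertainty where the exact 95% interval runs 0-71% (0/3) or 40-100% (4/4). The chance of this is about 12-37% with 3-4 children and 1-6% with 8. These figures rest on the usual SE formula, an assumed cohort size and assumed response rates of 50-70%.
- **Off-schedule values.** This part needs no assumption about size. As written, any value at 10 of the 12 post-baseline visits in F2.01, F2.04, T2.02 or T2.03 could come only from withdrawal or unscheduled scores. How many will occur cannot be judged from the documents, and there may be none.

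The reported Week 12 and Week 52 counts in T2.01 are unaffected. The change is worth making because it costs almost nothing.

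**What to change.** 1. In F2.04, and in F2.01 for consistency, replace ±SE with exact (Clopper-Pearson) 95% confidence intervals and show n at each point. Add the same intervals to T2.01.
2. Limit F2.01, F2.04, T2.02 and T2.03 to Weeks 12 and 52 post-baseline. State in SAP 7.1.4 that SLEDAI scores slotted to any other visit are listed only, in L2.01.

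The cost is an interval column in one table, a different interval in two figures, a visit restriction in four displays and one sentence of text. No new data are needed. The downside is that exact intervals are conservative and will look wide by cohort.

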7.2. Other Efficacy Analyses

7.2.1. Proteinuria

Proteinuria shifts from baseline will be summarized by visit [T2.04].

Baseline proteinuria data will be summarized as the number and percentage of subjects who are normal (≤0.5 mg/mg) or high (>0.5 mg/mg). For each post-baseline visit the data will be summarized by normal or high baseline status. Among subjects normal at baseline, the shifts presented will be 'No Change' or 'Normal to High'. Among subjects high at baseline, the shifts presented will be 'No Change' or 'High to Normal'.

As well as presenting the data for each visit, the proteinuria shifts will be summarized based on shifts at any time post-baseline. Among subjects with normal proteinuria at baseline, the number and percentage of subjects with at least one high post-baseline value will be presented as 'Normal to High'; subjects who never experience a high proteinuria value post-baseline will be presented as 'No Change'. Among subjects with high baseline proteinuria, subjects with at least one normal post-baseline value will be presented as 'High to Normal'; subjects who never experience a normal post-baseline value will be presented as 'No Change'.

No statistical tests will be performed.

7.2.2. Prednisone

For analyses, all corticosteroids are converted to a prednisone equivalent average daily dose (mg/day), therefore analyses refer to average daily prednisone equivalent dose instead of average daily steroid dose. The definition and derivation of this can be found in Section 13.4.4.

Prednisone data presented by visit will use the visit date recorded on the vital signs panel of the eCRF. These dates will then be used to assess the prednisone dose at that visit, using the derivations specified in Section 7.2.2.2 and Section 7.2.2.3.

A listing of daily prednisone dose will be provided for each subject by visit [L2.02]. The listing will present the average daily prednisone dose at the visit and the change from baseline in average daily prednisone dose in the 7 days prior to the visit (Section 7.2.2.3), as well as the average daily prednisone dose between visits and the change from baseline in average daily prednisone dose from the previous visit (Section 7.2.2.2).

7.2.2.1. Baseline Prednisone Dose

At baseline, the average daily prednisone dose is the sum of all prednisone doses over 7 consecutive days up to, but not including Day 1, divided by 7.

7.2.2.2. Average Daily Prednisone Dose Between Visits

The average daily prednisone dose between visits will be calculated for each scheduled post-baseline visit by summing all prednisone doses since the previous visit (previous visit date +1) up to and including the current visit and then dividing by the number of days in this period (Date of current visit – Date of previous scheduled visit). Days on which a subject does not have prednisone use recorded will be considered as 0 mg for the day in the calculation of average daily prednisone dose.

For subjects who withdraw from the study, the early withdrawal visit will only be presented if it slots into a scheduled visit (see Section 13.1.1).

